6.5. COMMON CALCULATIONS

Change from baseline will be calculated as:

• Change from baseline = Test value at post-baseline visit – Baseline value

Percent change from baseline will be calculated as:

• Percent change from baseline (%) = (Change from baseline at post-baseline visit / Baseline value) * 100%

Change from baseline for Illness Visits will be calculated as:

- Change from baseline at Illness Visit Day 1 = Test value at Illness Visit Day 1 Baseline value
- Change from baseline at Illness Visits after Illness Visit Day 1 = Test value at post Illness Visit Illness Visit baseline value

Percent change from baseline at Illness Visits will be calculated as:

- Percent change from baseline Illness Visit Day 1 (%) = (Change from baseline at Illness Visit Day 1/ Baseline value) * 100%
- Percent change from baseline at Illness Visits after Illness Visit Day 1 (%) = (Change from baseline at post-baseline Illness Visit / Illness Visit baseline value) * 100%

If baseline is not available, the change from baseline and percent change from baseline will not be calculated and will remain missing.

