6.2. BASELINE

Unless otherwise specified, baseline is defined as the last non-missing measurement taken prior to the dose of IMP. In the case where the last non-missing measurement and the date and time of the dose of IMP coincide or where time is missing, that measurement will be considered baseline, but adverse events (AEs) and medications commencing on the date and time of the dose of IMP will be considered post-baseline.

Illness Visit baseline is defined as the first non-missing measurement taken on Illness Visit Day 1. If there is no non-missing measurement available on Illness Visit Day 1, Illness Visit baseline is considered as missing. For instances where Illness Visit Day 1 occurs on the same day as a main study Visit, and Illness Visit Day 1 measurements are missing, then the measurements from the main study Visit will be used as Illness Visit baseline. Otherwise if there is still no available measurement for Illness Visit Day 1, Illness Visit baseline is considered as missing.

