16.3.1. EXPLORATORY EFFICACY ENDPOINTS

16.3.1.1. The Incidence of the First Case of SARS-CoV-2 RT-PCR-Positive Symptomatic Illness Occurring after Dosing with IMP through Day 366

An exploratory endpoint is the incidence of the first case of SARS-CoV-2 RT-PCR-positive symptomatic illness occurring after dosing with IMP through Day 366. The criteria for determining this endpoint is the same as those for the primary efficacy endpoint (see Section 16.1.1) except that the endpoint will only be evaluated within the specified efficacy evaluation period, through Day 366. The analysis will be performed on the full pre-exposure analysis set. This endpoint will be analyzed as described in Section 16.2.1.

To assess the durability of efficacy analyses for the incidence of the first case of SARS-CoV-2 RT-PCR-positive symptomatic illness occurring after dosing with IMP through Day 366, single-arm descriptive summaries over the Day 366 follow-up period for participants who received AZD7442 with no censoring for unblinding intercurrent events will be presented. However, if a participant receives a COVID-19 vaccine or COVID-19 preventive product, their follow-up will be censored at the date of first administration of that product.

16.3.1.2. Viral Genome Copies in NP Swabs Collected at Illness Visits as Determined by qRT-PCR

An exploratory efficacy endpoint is the viral genome copies in NP swabs which will be collected via SARS-CoV-2 RT-PCR test at central laboratory at Illness Visits as described in protocol section 1.3. The analysis will be performed on the full pre-exposure analysis set. Observed and change from baseline for Illness Visits (as defined in Section 6.5) in viral load will be summarized by planned treatment group and time points for the Illness Visits. A

logistic regression analysis of the proportion of participants with viral load $>10^4$ copies/mL may be performed. In addition, the number of weeks of high viral load ($>10^4$ copies/mL) among participants may be performed using a Stratified Wilcoxon rank sum test.

A listing will be provided for all viral genome copy data, regardless of RT-PCR result. Indicators will be included in listings of illness visits to distinguish those with positive RT-PCR results from those with negative RT-PCR results.

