16.3.1.3. Duration of SARS-CoV-2 Shedding in Saliva Over Time (Illness Visits only)

Viral Shedding

An exploratory efficacy endpoint is the duration of SARS-CoV-2 shedding in saliva over time. The analysis will be performed on the full pre-exposure analysis set. Saliva samples for viral shedding will be collected at Illness Visits as described in protocol section 1.3. The number and proportion of participants shedding on Illness Visits planned in the protocol Schedule of Assessments will be summarized. Exact 95% CIs using Clopper-Pearson method for binomial proportions will be computed.

The duration of SARS-CoV-2 shedding in saliva will be calculated as following:

Duration (days) = (Date of Illness Visit when viral shedding first tested as persistently negative or date of last Illness Visit when test was positive, if no negative test is available) – Date of first positive + 1.

The number of days of shedding will be summarized by descriptive statistics.

A listing will be provided for all viral shedding data, regardless of RT-PCR result. Indicators will be included in listings of illness visits to distinguish those with positive RT-PCR results from those with negative RT-PCR results.

• Viral Quantitation

For values reported as lower than the lower limit of quantification (LLOQ), a value equal to half of the limit of quantification will be imputed in viral quantitation summaries. Missing values will not be imputed in viral quantitation summaries.

For the subset of participants who shed, viral quantities as measured by qRT-PCR will be summarized for Illness Visits planned in the protocol Schedule of Assessments. Summary statistics will be presented describing the mean, standard deviation, median, minimum and maximum of Log10 (viral copies/mL) at Illness Visit baseline (Date of first positive) and each post-baseline time-points.

Change and percent change from Illness Visit baseline at each post-baseline time point will also be summarized.

Time weighted change from Illness Visit baseline to each post-baseline time-point is derived on a by-participant basis using the linear trapezoidal rule with all available data from baseline to that specific time-point minus the baseline value. This is defined as (Area Under the Curve [AUC])/number of days – Illness Visit baseline value, between Illness Visit baseline to that specific post-baseline time-point. AUC from Illness Visit baseline to each post-baseline time-point will be reported as well.

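### SAP 16.3.1.3 asks for percent change of a quantity it summarises only as log10 copies/mL, and its Illness Visit baseline does not match SAP 6.2

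*SAP*

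**What the plan says.** Four statements in the SAP bear on this.

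- **Scale (16.3.1.3, Viral Quantitation).** For participants who shed, the listed summary statistics are the mean, SD, median, minimum and "maximum of Log10 (viral copies/mL) at Illness Visit baseline (Date of first positive) and each post-baseline time-points". The figures planned for this output are also of log10 copies/mL.
- **Percent change (16.3.1.3).** The section then adds: "Change and percent change from Illness Visit baseline at each post-baseline time point will also be summarized". That sentence names no scale.
- **Formula (6.5).** For illness visits after Day 1, percent change is the ratio "Change from baseline at post-baseline Illness Visit / Illness Visit baseline value) * 100".
- **Baseline (6.2).** "Illness Visit baseline is defined as the first non-missing measurement taken on Illness Visit Day 1". A same-day main-study measurement may stand in. Otherwise, "If there is no non-missing measurement available on Illness Visit Day 1, Illness Visit baseline is considered as missing".

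For values below LLOQ, 16.3.1.3 says that "a value equal to half of the limit of quantification will be imputed in viral quantitation summaries". The SAP does not give the LLOQ.

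**The concern.** A difference of log10 values already expresses a proportional change: -2 log10 is a 99% fall wherever it starts. Dividing that difference by the log10 baseline brings the starting level back in, so participants with identical proportional clearance get different percentages. If the arms differed in saliva load at the start of illness, their percent-change columns would differ even with equal clearance.

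The second problem is the reference point. Section 6.2 anchors Illness Visit baseline to a visit day, and 16.3.1.3 anchors it to the date of first positive. Change, percent change, AUC and time-weighted change in 16.3.1.3 all start from that baseline. Two programmers, each able to cite the SAP, could include different participants and report different values for the same participant.

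**Working it through.** The SAP gives no numerical result here, so there is no figure to reproduce. The check applies its own rules to illustrative values.

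**Step 1: percent change on the log10 scale.**

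Inputs: the 6.5 formula, the log10 copies/mL scale of 16.3.1.3, and a 99% fall (post = 0.01 × baseline). The starting levels are assumptions. The level 10^4 appears in the SAP only as a nasopharyngeal (NP) swab threshold in 16.3.1.2 ("logistic regression analysis of the proportion of participants with viral load $>10^4$ copies/mL may be performed"). All values are assumed above LLOQ, which for the last row means an LLOQ below 10^2 copies/mL.

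Formula: 100 × (log10 post - log10 baseline) / log10 baseline = 100 × (-2) / log10 baseline.

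| Baseline to post (copies/mL) | Percent change in copies | Change in log10 | Percent change of log10 |
|---|---|---|---|
| 10^8 to 10^6 | -99% | -2 | -2/8 = -25.0% |
| 10^6 to 10^4 | -99% | -2 | -2/6 = -33.3% |
| 10^4 to 10^2 | -99% | -2 | -2/4 = -50.0% |

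Read the other way, a reported -25% from 10^8 is -2 log10 (a 99% fall), while from 10^4 it is -1 log10 (a 90% fall). The second and third columns do not depend on the starting level; the last one does.

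**Step 2: where the two baselines part.**

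- Day 1 saliva positive: the date of first positive is Day 1, so the definitions agree. This includes a Day 1 sample that is positive but below LLOQ.
- Day 1 saliva missing, later sample positive: 6.2 gives no baseline unless a same-day main-study value exists, and 6.4 lists saliva only under the illness schedule. The participant has no change value under 6.2 but has one under 16.3.1.3.
- Day 1 saliva negative, later sample positive: 6.2 uses the Day 1 value and 16.3.1.3 uses the later one.

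The last two cases can occur. Under 16.1.1 a case is determined on the NP swab, with saliva only a fallback, so an RT-PCR-positive illness need not have positive saliva on Day 1.

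**Step 3: size of the baseline difference in one episode.**

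Assumed values: Day 1 negative and entered as LLOQ/2, 10^6 on Day 3 (first positive), 10^4 on Day 14, no other samples. The LLOQ is varied because it is not stated.

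| Assumed LLOQ (copies/mL) | Log10 baseline, 6.2 | Day 14 change, 6.2 | Day 14 change, 16.3.1.3 |
|---|---|---|---|
| 10 | 0.70 | +3.3 | 4 - 6 = -2.0 |
| 100 | 1.70 | +2.3 | -2.0 |
| 500 | 2.40 | +1.6 | -2.0 |
| 1000 | 2.70 | +1.3 | -2.0 |

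Time-weighted change is AUC divided by days, minus baseline. For LLOQ 100:

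- From Day 1: AUC = 2 × (1.70 + 6)/2 + 11 × (6 + 4)/2 = 7.7 + 55 = 62.7. Then 62.7/13 - 1.70 = 4.82 - 1.70 = +3.1.
- From Day 3: AUC = 11 × (6 + 4)/2 = 55. Then 55/11 - 6 = -1.0.

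In this episode both measures change sign with the choice of baseline.

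**The case against.** The strongest reply is that 16.3.1.3 never says percent change is taken on log10 values. Its paragraph opens with viral quantities measured by qRT-PCR, the log10 label belongs to the list of summary statistics, and the percent-change sentence stands apart. If percent change were computed on copies, each row in Step 1 would read -99% and the scale problem would vanish. This is fair as far as it goes: the log10 scale is inferred from context. But log10 is the only scale the section describes, so it is the natural reading, and the sentence needs a scale either way.

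On the baseline, one can say that analysis-specific wording overrides a general definition. That is common practice, but the SAP states no order of precedence here. The proviso in 6.2 that allows exceptions is attached to the main-study baseline, not to the illness one.

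Three stronger readings are tempting but not supported:

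- A reader might infer that any Day 1 value below LLOQ reverses the sign of change. It does not: a positive but unquantifiable Day 1 sample gives the same baseline under both definitions. The reversal in Step 3 needs a negative Day 1 sample that is still entered at LLOQ/2, and the SAP does not say how negatives are valued.
- A reader might object that percentages of log10 values also shift with the concentration unit, or are undefined at a log10 baseline of 0. The SAP fixes the unit as copies/mL, and a zero baseline means 1 copy/mL, which under LLOQ/2 imputation would need an LLOQ of 2 copies/mL or less. Neither is a practical problem in this plan.
- A reader might infer that a treatment comparison is compromised. Section 16.3.1.3 describes no between-arm test of percent change.

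**Conclusion.** The point holds as a minor one. On the natural reading of 16.3.1.3 with 6.5, percent change divides a log10 difference by a log10 baseline. The reported figure for one and the same 99% fall then runs from -25% to -50% over starting levels from 10^8 to 10^4 copies/mL. This rests on the inferred log10 scale and on illustrative levels above LLOQ.

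Separately, 6.2 and 16.3.1.3 define Illness Visit baseline differently, with no rule to choose between them. The difference matters only when Day 1 saliva is negative or missing and a later sample is positive. The documents do not say how often that will be.

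The reach is small: an exploratory, descriptive saliva output. Log10 change is already planned and escapes the scale problem, though not the baseline conflict. The primary and key secondary analyses do not use this calculation, and 16.3.1.2 asks for no percent change of NP-swab viral load.

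**What to change.** In 16.3.1.3:

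- Delete percent change of log10 values. Report change in log10 copies/mL, with the mean change and its 95% CI back-transformed to a geometric mean fold change, as 17.1.4 already does for neutralising antibody titres. If a percentage is wanted, state that it is computed on the copies scale.
- State one Illness Visit baseline for saliva viral quantitation and make 6.2, 6.5 and 16.3.1.3 agree. One option is to keep the first-positive baseline and write it into 6.2 as an explicit exception. A Day 1 baseline is also possible, but it drops participants without a Day 1 sample and, in the Step 3 episode, shows a rise for someone whose load fell from 10^6 to 10^4. The choice is the sponsor's; what matters is that there is only one.
- Say what value a negative saliva sample takes in these summaries.

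The cost is a few lines of SAP text and one table column removed or relabelled. No new data are needed.

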7. STATISTICAL CONSIDERATIONS

For continuous data, descriptive statistics (i.e., n [number of participants with available data], mean, standard deviation [SD], median, minimum, maximum, and quartile values) will be presented by treatment group and visit, when applicable. For concentration data and log-transformed data, descriptive statistics (i.e., n [number of participants with available data], n < lower limit of quantification (LLOQ) [number of participants with results below the limit of quantification], geometric mean, arithmetic mean, SD, co-efficient of variation, median, min and max) will be presented by treatment group and visit, when applicable.

For categorical data, the number and percentages of participants in each category will be presented by treatment group and visit, when applicable. The denominator for percentage calculation is the underlying analysis set population unless otherwise stated.

7.1. SAMPLE SIZE CALCULATION

Approximately 5150 participants will be randomized in a 2:1 ratio to receive a single IM dose of AZD7442 (divided in 2 sequential injections, one for each mAb component) (the active group, n = approximately 3433) or saline placebo (the control group, n = approximately 1717) on Day 1.

The sample size calculations are based on the primary efficacy endpoint and were derived following a modified Poisson regression approach (Zou 2004). All participants will be followed for the entire duration of the study.

With at least 18 observed events, assuming 80% true efficacy, the study will have approximately 90% power to demonstrate that the lower bound of the 2-sided 95% CI for efficacy is greater than 0 (see Table L:).

Table L: Simulated Power by Number of Observed Events

$\lambda_{Placebo}$	$\lambda_{AZD7442}$	Observed Events	Simulated Power
0.0074	0.0015	18	89%
0.0082	0.0016	20	96%
0.0090	0.0018	22	97%
0.0098	0.0020	24	98%

Simulated power is based upon 10000 simulations of trials assuming 80% efficacy $\left(1 - \frac{\lambda_{AZD7442}}{\lambda_{Placebo}}\right)$, using Poisson regression model with robust variance, with no participants lost follow-up. Power is the proportion of trials with p-value < 0.05.

The sample size necessary to achieve the power for the primary endpoint is calculated based on the assumed attack rate in the placebo group and the 80% efficacy assumption, using Poisson regression model with robust variance.

7.2. MISSING DATA

Missing efficacy data will be handled as described in Sections 16.1.2, 16.2.4, and 16.3.2 of this analysis plan.

Partially or completely missing medication dates will be handled as described in APPENDIX 1.

7.3. STATISTICAL TESTS

Statistical tests will be conducted at the two-sided 5% significance level. Confidence Intervals (CIs) will be two-sided with 95% coverage.

The null hypothesis for the primary endpoint is: efficacy of AZD7442 compared to placebo in preventing COVID-19 is equal to 0. Whereas, the alternative hypothesis is: efficacy of AZD7442 compared to placebo in preventing COVID-19 is not equal to 0. That is:

H0: efficacy = 0

HA: efficacy $\neq 0$

Primary efficacy will be presented with a 2-sided 95% CI, and statistical significance will be achieved if the lower bound of the 2-sided 95% CI is > 0. The success criterion for the study will be statistical significance.

If the statistical significance of the primary efficacy endpoint is demonstrated at two-sided alpha of 0.05, formal assessments of the key supportive estimands and key secondary estimand will be conducted at the primary analysis.

7.4. MULTIPLE COMPARISONS/ MULTIPLICITY

A hierarchical approach will be used to control for multiplicity of the primary, key supportive, and key secondary analyses. That is, the null hypotheses for these efficacy analyses will be tested in a hierarchical order, and the

subsequent null hypothesis will be tested at a significance level of 0.05 (two-sided) only if the prior null hypothesis is rejected (i.e., the treatment effect on the efficacy endpoint is demonstrated at the significance level of two-sided 0.05). The hierarchical approach will include the below analyses as ordered:

- The primary efficacy endpoint will be assessed at the primary analysis, using the primary estimand, after approximately 24 primary endpoint events have been confirmed or 30% of study participants have become unblinded, whichever occurs earlier. All primary endpoint events accrued up until data cut-off will be included in the primary analysis.
- 2. If the statistical significance of the primary efficacy endpoint is demonstrated at 2-sided alpha of 0.05, a formal assessment of the primary endpoint using the first key supportive estimand (treatment policy strategy) will be conducted also at the primary analysis.
- 3. If the statistical significance of the first key supportive analysis of the primary endpoint is demonstrated at 2-sided alpha of 0.05, a formal assessment of the primary endpoint using the second key supportive estimand (including death due to any cause) will be conducted also at the primary analysis.
- 4. If the statistical significance of the second key supportive analysis of the primary endpoint is demonstrated at 2-sided alpha of 0.05, a formal assessment of the key secondary efficacy endpoint will be conducted also at the primary analysis.

Only nominal p-values will be provided for the other secondary and exploratory efficacy endpoints. No statistical testing will be performed for the safety endpoints.

7.5. MULTICENTER STUDIES

This study will be conducted by multiple investigators at multiple centers internationally. Data from all centers will be pooled together in the analyses and there are no plans to perform an analysis of homogeneity of the results across centers.

7.6. ADJUSTMENTS FOR COVARIATES AND FACTORS TO BE INCLUDED IN ANALYSES

The analyses will be adjusted for the following covariates and factors. For details of their inclusion in the models, refer the Sections 16.1.3 and 16.2.5.

• Categorical age (years) at randomization from the Electronic Data Capture (EDC) system (\geq 60 and < 60).

7.7. EXAMINATION OF SUBGROUPS

Subgroup analyses will be conducted as stated in Section 16.1.7. It should be noted that the study was not designed to detect treatment differences with high statistical power within subgroups.

The list of subgroups includes but may not be limited to:

- Categorical age (years) at informed consent (3 groupings 1: ≥60 years and <60 years, 2: ≥65 years and <65 years, 3: ≥75 years and <75 years);
- Residence in long-term care facility (yes and no);
- Increased risk of exposure to infection with SARS-CoV-2 (yes and no);
- Increased risk for inadequate response to active immunization (yes and no);
- Sex (male and female);
- Region (North America, United Kingdom, and European Union);
- Country (United States, United Kingdom, Belgium, France, Spain);
- Race (American Indian or Alaska Native, Asian, Black or African American, Native Hawaiian or Other Pacific Islanders, White);
- Ethnicity (Hispanic or Latino, Not Hispanic or Latino);
- COVID-19 co-morbidities at baseline (at least one co-morbidity, no co-morbidity);
- High Risk for severe COVID-19 at baseline (History of Obesity, Obese (baseline BMI≥30), Morbid Obesity (baseline BMI≥40), Chronic kidney disease (CKD), Diabetes, Immunosuppressive disease, Immunosuppressive treatment, Cardiovascular disease (CV disease), Chronic obstructive pulmonary disease (COPD), Chronic liver disease, Hypertension, Asthma, Cancer, Smoking, Sickle cell disease) (yes/no; refer to APPENDIX 1 for description of each condition).

If models of subgroup analysis do not converge due to sparse data, changes to planned subgroup analysis will be described in the CSR.

Subgroup data will be obtained from the EDC system for items collected in both EDC and Interactive Response Technology (IRT).

7.8. SOFTWARE VERSION

All analyses will be conducted using SAS version 9.4 or higher.

8. OUTPUT PRESENTATIONS

APPENDIX 2 shows conventions for presentation of data in outputs.

The templates provided with this SAP describe the presentations for this study and therefore, the format and content of the summary tables, figures, and listings to be provided by IQVIA Biostatistics.

9. DISPOSITION AND WITHDRAWALS

All participants who provide informed consent will be accounted for in this study.

9.1. DISPOSITION

Number of participants screened will be presented overall for the PAS. Number and percentage of participants with screen failure and reason for screen failure will also be presented overall based on the PAS. Number of participants randomized will be presented overall and by treatment group for the PAS.

Number and percentages of participants dosed, discontinued early from IMP (including reason for not receiving both injections), ongoing in study (for primary analysis only), who discontinued early from the study (including reason for withdrawal), and who became unblinded to received treatment (including reason for unblinding) will be provided overall and by planned treatment group based on the FAS.

The number of participants included and excluded from each analysis set (including reason for exclusion) will be summarized overall and by planned treatment group based on the FAS. A listing showing inclusion and exclusion of each participant from each analysis set, including reason for exclusion, will be provided.

